Study Rationale	While e-cigs are commonly represented as safer alternatives to tobacco cigarettes, little is known regarding the health effects of their short- or long-term use. The responses and the e-cig components exerting these effects on the airways are largely unknown. Hence, a critical need currently exists in identifying e-cig components, namely specific flavors, modifying respiratory immune responses.		
Study Objective(s)	Primary		
	• Determine the effects of CA-containing e-cigarettes on airway epithelial cell ciliary function (i.e. MCC) in vivo		
	Secondary		
	 Baseline differences in MCC in non-smokers/non-vapers as compared to e-cigarette users Differential cell counts in CA-induced changes in IS samples 		

• Regional lung clearance rates via MCC scan.

Test Article(s) (If Applicable)	An e-cigarette that contains CA-containing flavors.
Study Design	This will be a blinded, crossover study to assess the effect that vape liquid containing cinammaldhyde (CA) has on the innate mucosal immune system of current users of e-cigarettes. The primary endpoint will be the effect of the CA-containing e-cigarette liquid on airway epithelial cell ciliary function, in vivo. The primary analysis will be achieved via the mucociliary clearance (MCC) scan.
	Prior to enrollment, subjects will be screened based on their ability to produce sputum with sufficient viable cell counts for analysis as well as their history of radiation exposure. Study visits thereafter will include a baseline visit for both the vape/non-vape cohorts to measure baseline MCC, epithelial lining fluid (ELF), induced sputum (IS), blood values, and urine. The e-cigarette cohort will have a total of seven visits, and the control cohort with 3 visits.
Subject Population	Inclusion Criteria
	1. Subjects age 18-40

key criteria for Inclusion and Exclusion:	2. Subjects who currently use a vaping device and an equal number of subjects who do not use a vaping device		
	Exclusion Criteria		
	3. Any pre-existing lung disease (asthma, cystic fibrosis)		
	4. Any significant chronic illness, such as, but not limited to, heart disease, uncontrolled hypertension, diabetes, auto-immune disease		
	5. Any use of tobacco products (other than e-cig) in the past 3 months, or a greater than 10 pack year history of smoking cigarettes.		
	6. Pregnant or nursing women		
	 Subjects with a history of radiation exposure in the past year which exceeds annual safe limits. 		
Number Of Subjects	Total Number of Subjects: 54 total, 22 who currently vape, 32 who do not vape (data from n=12 subjects of this group already exist from a previous study)		
Study Duration	Each subject's participation will last up to 3 months. There is a 2-6 week washout each session.		
	The entire study is expected to last up to 3 years.		
Study Phases Screening Study Treatment Follow-Up	(1) Screening : After informed consent is obtained, a medical history, including medication use and radiation history, will be obtained. Spirometry will be collected, and subjects will undergo sputum induction procedure. Subjects must produce an adequate sputum (based on cell counts and viability) in order to continue in the study.		
	(2) Intervention : Subjects who successfully complete all screening procedures will return to the study lab and undergo an ELF collection, blood, urine, and MCC/sputum induction. Subjects will return approximately. 24 hours later for a follow up MCC scan to undergo sputum induction again. At this point, participation ends for all non-vaping subjects. Subjects who vape will continue their visit with a training session with the lab's e-cigarette device, as well as their own. Subjects will return within 2 to 6 weeks and repeat the vaping session, with randomized e-liquid. Subjects will then undergo MCC scan followed by epithelial lining fluid (ELF) collection and induced sputum. Subjects will return the next day for a 24 hour follow up scan, epithelial lining fluid (ELF) collection, blood draw, urine collection, and sputum induction. There will a 2-6 week washout, and the subject will return to repeat the session, vaping the randomized e-liquid.		
Efficacy Evaluations	NA		
Pharmacokinetic Evaluations	NA		
Safety Evaluations	Subject safety is monitored throughout the study with vital signs and spirometry, as well as urine pregnancy testing prior to each MCC scan.		
	_		

Statistical And Analytic Refer to section 5.2 Plan

DATA AND SAFETY Monitoring Plan	Describe who is responsible for data quality management and ongoing assessment of safety: PI, independent medical monitor, internal safety committee, or DSMB. Case report forms to collect data will be developed by the study team. Identifiable data (name, contact information) is
	kept on a form separate from the research data, however all forms will have the study number. All paper data will be maintained by the study coordinator or the investigators, and will be kept in locked offices during non-business hours. REDCap is trackable by ONYEN, access to identifiers will only be given to those who need it to do their job. Subjects are monitored in real time during all procedures, and an MD is always available during the inhalations of the e-cig and for the TC99 inhalations. An MD is also immediately available for all sputum induction procedures. The PI will be responsible for the data management, and the PI, along with a study physician, will be responsible for the subject safety assessments.

1 BACKGROUND AND RATIONALE

"Vaping" flavored electronic cigarettes (e-cigs) is gaining popularity in the U.S., particularly among teens and young adults. Availability of different flavorings is often cited as the main reason among youth/adolescents to try e-cigs, yet the recent Surgeon General's report focused on nicotine addiction as the main health concern. There are currently more than 7,700 commercially available flavored e-cig liquids (e-liquids), which contain food-safe flavorings without significant data on potential inhalation toxicity. Common e-liquid flavorings contain aliphatic aldehydes for fruity flavors and α , β -unsaturated aldehydes, such as cinnamaldehyde (CA), for spicy flavors. Spicy or cinnamon-flavored e-liquids are popular and frequently identified as "Best Sellers" by e-liquid retailers.

While e-cigs are commonly represented as safer alternatives to tobacco cigarettes, little is known regarding the health effects of their short- or long-term use. We have previously demonstrated that cigarette smoking significantly affects innate immune function of the respiratory mucosa by modifying mucosal immune cell function, immune gene expression, and mucociliary clearance (MCC), thereby potentially enhancing susceptibility to respiratory infection. We have previously demonstrated that suppression of immune gene expression was significantly greater in the upper airways/nasal mucosa of e-cig users as compared to non-smokers and cigarette smokers, but the mechanisms mediating these responses and the e-cig components exerting these effects are largely unknown. Hence, a critical need currently exists in identifying e-cig components, namely specific flavors, modifying respiratory immune responses.

We will use innovative translational research models to examine how one leading popular flavoring component, CA, modifies respiratory mucosal immune responses. Yet, how CA could affect respiratory immune responses *in vivo* in humans is unknown, which is the overall objective of this study. The feasibility of our proposed

studies is supported by preliminary data demonstrating that CA 1) inhibits immune cell function in vitro and reduces ciliary beat frequency on airway epithelial cells in vitro. Thus, based on these data we hypothesize that **CA-containing e-liquids suppress innate mucosal immune function in humans in vivo.** We will use integrated translational research models and our unique capability of assessing MCC and induced sputum airway immune cells in humans *in vivo* for this study.

Introduction

1.1 Name and Description of Investigational Product or Intervention

Each vaping session will occur with a vaping device (The Vapor Shark DNA 250), which allows manual control and recording of the vapor settings (voltage, wattage, puff volume, and puff frequency), using the myVaporsTM software. Data can be directly imported into a database, thus allowing detailed information of a very controlled vaping session. To reduce variability, subjects will be asked to use the e-cig device (The Vapor Shark DNA 250) and e- liquids provided by us for the indicated vaping sessions. Please note, we are not studying the device, we are simply using it to deliver the e-liquid in a controlled fashion.

Subjects will vape with two different e-liquids (one completely devoid and one containing at least 30mM CA similar to the commercially available "Hot Cinnamon Candies" flavor. These e-liquids will be purchased from a local vaping shop.

Non-Clinical and Clinical Study Findings

-Potential Benefits: There are no direct benefits to the subject. Society benefits by understanding potential adverse health effects induced by exposure to e-cigarette aerosols containing specific flavoring chemicals.

-Risk /Benefit Assessment: The radiation exposure is within safe limits for healthy adults. The effective dose for the three measures of MCC (including Co57 transmission scans) is approximately 133 mRem. This is less than the natural environmental radiation that adults receive every year, which in Chapel Hill is about 300 mRems. The risk from the radiation dose received from this procedure is too small to be detected. Urine pregnancy tests will be done prior to each measurement of MCC as there is no safe risk to a fetus for this investigational study. Women with a positive pregnancy test, or those who do not use a reliable form of birth control will not be included. Spirometry and sputum induction carry a risk for wheezing, which is uncommon in healthy individuals. Only subjects who currently use an e-cigarette will be recruited for the active part of the study, e-cig naïve individuals will not be intentionally exposed. Despite the investigational nature of this study, the risk of the 3 separate vaping sessions are not more than the risk subjects take when they vape outside this study.

1.4 Relevant Literature and Data

Recent studies demonstrated that e-cig vapor exposure decreases antimicrobial and phagocytic function of immune cells resulting in reduced bacterial clearance and increased bacterial burden in the lung. Aldehydic flavoring compounds, such as CA have reported immunomodulatory function in immune cells, such as macrophages (Macs), including anti-inflammatory properties, decreased ROS/RNS formation, and alteration in immune cell surface marker expression. Most of these studies were conducted in non-human cell lines without direct relevance to the lung and did not reveal biochemical mechanisms mediating these effects. In our lab we recently demonstrated that Macs obtained from healthy volunteers via bronchoalveolar lavage (BAL) and exposed to the CA- containing e-liquid "Sini-cide" ex vivo almost completely blocked phagocytosis and the ability to engulf BioParticles® (Clapp et al., 2017). In addition to "Sini-cide", we screened popular e-liquids purchased from a local vape shop and found additional e-liquids containing between 900µM-1M CA ("Kola", "Hot Cinnamon Candies", and "Sini-cide"). Exposure of Macs to other CA-containing e-liquids ("Hot

Cinnamon Candies") also decreased phagocytic function in Macs, a response that could be mimicked by treating cells with CA alone in a dose-dependent manner, indicating that CA alone has direct inhibitory effects on Mac phagocytosis at levels that are not cytotoxic (Clapp et al., 2017). Other components of the upper respiratory tract that are essential innate defense mechanisms include the mucosal barrier and mucociliary clearance (MCC). In MCC, motile cilia beat in a coordinated fashion to move airway mucus toward the larynx. This complex process relies on the structure, number, and coordinated movement of airway cilia. Dysfunction of the coordinated beating of cilia and impaired MCC is associated with significant airway disease. Our preliminary data demonstrate that exposure of differentiated well-ciliated human bronchial or nasal epithelial cell (HBECs or HNECs) to e-liquids containing the flavoring chemical cinnamaldehyde (CA) ("Sini-cide"), or CA alone causes acute, yet reversible, ciliary stasis. Hence, acute exposure of CA-flavored e-cigs impairs ciliary beating, which could translate into significant effects on MCC in humans in vivo.

2 STUDY OBJECTIVE

The overall objective of the study is to determine the effects of CA-flavored e-cigarettes on MCC and airway immune cells in vivo. To achieve this objective, the study will address the following specific aims:

Aim 1. Characterize and compare two cohorts (current non-vaping controls and current e-cig users) in terms of baseline characteristics and measures of MCC and measures of immune cell function.

Aim 2a.Evaluate the effects of CA on ciliary function in terms of measures of MCC in current e-cig users.Aim 2b.Evaluate the effects of CA on airway immune cells obtained through induced sputum (IS) in current e-cig users.

3 INVESTIGATIONAL PLAN (brief overview)

3.1 Study Design

We will evaluate the acute effect of CA-flavored e-cigs on MCC and IS immune cells in up to 22 healthy, young adults who are current e-cig users with a total of less than 10 pack-years cigarette smoking history. MCC will be measured by gamma scintigraphy at baseline and following controlled vaping of e-liquids with and without cinnamon flavoring. Two different e-liquids (one completely devoid and one containing at least 30mM CA similar to "Hot Cinnamon Candies" which is commercially available) will be used for two separate randomized vaping sessions. The randomization scheme for the two different e-liquids (e-liquids with and without CA) will be generated by using the Web site Randomization.com (http://www.randomization.com), assigned treatment Regimen A and B by an assigned study team member, and provided to the study team. This individual will also be responsible for loading the e-cigarette with the appropriate solution for that session prior to the vaping sessions. n

We will also recruit non-vaping control subjects (n=22), who will only undergo the baseline testing and thus serve as a non-exposed/non-vaping control group. We will aim to recruit similar numbers of males and females in both cohorts. While we cannot guarantee age-matching and sex-matching in these cohorts, based on our previous studies (Martin et al., 2016), we do not expect to find significant age and sex differences in the two cohort. In addition, potential confounders, such as age, sex, and BMI will be included as covariates in our multivariate analysis. Observations obtained from the non-vaping control group will provide necessary information on potential baseline differences in the two cohorts (i.e. current vapers versus non-vaping controls). These data from the non-vaping control group are important to provide a reference for any potential CA-induced changes in the vaping group. Hence, there are two stages of the study:

Stage 1. A cross sectional observational cohort comparison of baseline MCC and IS immune cells in a reference cohort of n=22 non-vaping control subjects and E-cig cohort of n=22 currently vaping subjects (confounding based on other variables such as BMI, sex, age is possible for this stage).

Stage 2. A randomized comparison of changes in MCC and IS immune cells after Regimen A (e-cig us without CA) and Regimen B (e-cig use with CA). The cohort of e-cig users will undergo a randomized 2-treatment, 2-period, 2-sequence crossover study of CA exposure.

For stage 1, baseline measurements of Tc99m-SC clearance will be used to measure each subject's normal baseline MCC and IS immune cell characteristics. For both stages, subjects will be asked to complete a vaping diary to record information on the device and e-liquids (name/vendor/e-liquids/puffs/device settings) used during their normal vaping sessions for the entire duration of the study. In addition, for stage 2, subjects will be asked to maintain their current habits for the duration of the study, not to significantly increase or decrease their vaping patterns, including the nicotine concentrations of their e-liquids

For stage 2, for each e-cig vaping session (Training and MCC Test Days), subjects will be asked to follow a laboratory-based protocol involving 6, 5-minute paced vaping segments (1 puff/minute) over a 1 hour time period, vaping the e-liquid with and without CA provided by us. On each Test Day, subjects will undergo the vaping protocol immediately prior to inhalation of the Tc99m-SC (10 min between end of vaping and inhalation of Tc99m-SC). An initial deposition scan of Tc99m-SC will then be obtained followed by dynamic imaging of the lung with subjects seated in front of the gamma camera to determine potential changes in MCC induced by acute exposure to CA-flavored e- cigarettes. Induced sputum samples will be collected at baseline, and after each MCC scan, and app. 24 hours after completion of the MCC scans.

The two randomized vaping sessions will be separated by 2-6 weeks. While there are no data providing specific information on the duration needed to washout the effects of CA on MCC, previous studies examining changes in MCC following inhalation of other aerosols have shown that this washout period is sufficient to prevent potential carryover between the two treatments (Burbank AJ, 2017).

3.2 Allocation to Treatment Groups and Blinding (if applicable): The e-liquid will be randomized for either CA containing flavoring or non-CA containing fluid. Each vaping subject will crossover at the second session. Subjects and as well as personnel involved in the MCC and other analyses will be blinded to the CA or non-CA.

3.3 Study Duration, Enrollment and Number of Subjects 22 e-cig users, and 22 non-e-cig users will be recruited into the observational phase (stage 1) of the study. Each subject will have a screening visit followed by a baseline visit with an MCC scan. After the baseline/MCC scan visit, the subject will return within approximately 24 hours for a follow up MCC scan and a sputum induction. The non-e-cig users are completed at this point (note: data from 12 previously studies non-e-cig users will be included in the overall data analysis). The subject in the e-cig cohort will return the next day for a follow up scan/sputum induction as well as a training session with our e-cigarette device/lifeshirt. There will be a 2-6 week washout and then the vaping/MCC/SI session. The entire study should be concluded in no more than 3 years.

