The calculated power for the MCC comparison between vapers (e-liquid users) and non-vapers (healthy adult nonsmokers) will be based on the baseline MCC in n=20 for the former and n=32 for the latter (12 subjects studied recently in Bennett et al 2015 and an additional 20 non-vaping subjects here). The proposed difference in MCC (Ave90Clr) between the two groups is 4.5%, a chronic effect similar to the acute hypothesis above and $\frac{1}{2}$ of the relative difference seen between healthy adults and patients with chronic bronchitis with FEV1<40% pred (Anderson et al). From Bennett et al (2015) the mean baseline for health nonsmoking adults was 16% (+/-6). To observe the 4.5% absolute difference between the two groups we will have a power of 0.75 with a type I error of 0.05. It is unlikely that we will observe the 4.5% change both acutely (discussed above) and chronically, i.e. chronic effects of CA in vapers may mask the effect of a single dose of CA or the baseline MCC may be normal in vapers but slow with each acute dose of CA e-liquids. Studying both the single dose effect within the vapers (repeat comparisons) and the baseline differences between vapers and non-vapers (group comparison) will allow for a more complete picture of e-cigarette effects on MCC. These are the first studies to assess the effect of e-cigarettes on MCC in healthy adult subjects.

To assure that we would have sufficient power to determine statistically significant differences in IS cells in the proposed studies, we used preliminary data obtained from SI immune cells from non-vaping controls and e-cigarette users. In this study, the mean percentage of macrophages with high inflammatory markers in non-smokers was 20.8 with a standard deviation of 24.66. Assuming a difference between baseline and treatment group to be a 2-fold increase in percent macrophages with high inflammatory markers, which we saw in samples obtained from e-cigarette users, we will have a power of 0.965 with a type I error of 0.05 using the sample size of n=20 determined for MCC above.

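### The secondary vaper versus non-vaper MCC comparison pools 12 controls from an earlier study with about 20 concurrent ones, and no concurrent-controls-only estimate is planned beside it

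*Combined protocol and SAP*

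**What the plan says.** The synopsis (Number of Subjects) plans 32 non-vapers and notes that "data from n=12 subjects of this group already exist from a previous study". Section 3.3 says "22 e-cig users, and 22 non-e-cig users will be recruited into the observational phase" and adds that "data from 12 previously studies non-e-cig users will be included in the overall data analysis". Section 3.1 describes Stage 1 differently, as a "reference cohort of n=22 non-vaping control subjects and E-cig cohort of n=22 currently vaping subjects", without mentioning the earlier 12.

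Section 5.4 sets the power of this comparison "based on the baseline MCC in n=20 for the former and n=32 for the latter", the 32 being the 12 from the earlier hypertonic saline study "and an additional 20 non-vaping subjects here". It gives the target in a named metric: "The proposed difference in MCC (Ave90Clr) between the two groups is 4.5" per cent.

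Section 5.3 analyses Stage 1 by ANOVA on baseline MCC, with age, BMI and sex as covariates. The sensitivity analyses it lists concern the Stage 2 crossover model. On comparability, section 5.4 says only that the earlier healthy subjects were measured with the methods described in this protocol. The Primary Endpoint text of section 5 defines MCC as an average over 10 to 120 minutes; section 5.4 defines Ave90Clr as an average over 10 to 90 minutes.

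**The concern.** The earlier data sit on one side of the comparison only. If baseline MCC in the earlier study differed systematically from what the same kind of volunteer would show now, because of equipment, operators, selection or the clearance window used, part of that shift would appear as a chronic effect of vaping or would hide one. Adjusting for age, BMI and sex cannot remove a shift of that kind. The documents also do not say whether the 12 met the present age, spirometry and adequate-sputum requirements.

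The comparison is secondary, but it is Aim 1, the first-listed secondary endpoint, and has its own power statement. As planned, a reader of the result could not tell how far it depends on the 12 earlier subjects.

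**Working it through.** **Inputs.** From section 5.4: 20 vapers, 32 non-vapers (12 earlier, 20 new), target difference 4.5 points, baseline 16% (+/-6), α 0.05, stated power 0.75. Two assumptions: the 6 is a standard deviation, and the test is two-sided. Both are supported by the next step.

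**1. The plan's own power.** SE = 6 × √(1/20 + 1/32) = 1.71. By the normal approximation, power = Φ(4.5/1.71 − 1.96) = 0.749, which reproduces the stated 0.75. The two-sided t calculation gives 0.73; a one-sided t-test gives 0.83 and does not match.

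**2. How much of a shift enters.** If the earlier controls differ from concurrent ones by D points on average, the pooled control mean moves by (12/32) × D = 0.375 D. If all 22 new controls complete and the 12 are added, the weight is 12/34 = 0.353.

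**3. Effect for assumed D.** The documents give no value for D, so a range is shown. Type I error comes from simulated two-sample t-tests (20 v 32, SD 6, 200,000 replicates per row).

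| Assumed D | Bias = 0.375 D | Bias / 4.5 | Type I error |
|---|---|---|---|
| 2 | 0.75 | 17% | about 7% |
| 3 | 1.1 | 25% | about 9% |
| 4 | 1.5 | 33% | about 12% |

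The simple formula P(|Z + bias/SE| > 1.96) gives 7%, 10% and 14%. It runs high because a shift inside the control group also inflates the pooled SD: the added sum of squares is 32 × 0.375 × 0.625 × D² = 7.5 D² on 50 degrees of freedom. At D = 4 the SD becomes √(36 + 120/50) = 6.20. The simulated figures allow for this. If the drift opposes a true 4.5-point effect, simulated power falls to about 0.57 at D = 2 and 0.38 at D = 4.

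**4. Concurrent controls only.** At 20 v 20, SE = 6 × √(1/20 + 1/20) = 1.90 and power is 0.64 by t (0.66 normal). At 22 v 22, SE = 1.81 and power is 0.68 by t (0.70 normal).

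**5. What an old-versus-new comparison can show.** At 12 v 20, SE = 6 × √(1/12 + 1/20) = 2.19. The 95% half-width is 2.04 × 2.19 = 4.5 points, as wide as the target effect. Power to detect a drift is 0.14 at D = 2 and 0.42 at D = 4. With no drift at all, the pooled and concurrent-only estimates differ by chance with SD 0.375 × 2.19 = 0.82, more than the 0.75 bias at D = 2.

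**6. Control count.** Section 3.1 gives 22; the synopsis and section 5.4 give 32 including the 12; section 3.3 gives 22 new plus 12, that is 34, or 32 if 20 of the 22 complete.

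**The case against.** The strongest reply is that nothing in the documents shows any drift. Section 5.4 says the earlier subjects were measured by the same methods, a modest drift of 2 points moves the estimate by one sixth of the target, and this is a secondary endpoint in an observational stage whose confounding section 3.1 already acknowledges. All of that is true and limits the weight of the point. It does not replace a check: the statement about methods is an assertion, and it does not cover who was eligible.

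A reader might infer that drift passes into the difference in full. It does not; the concurrent controls dilute it to 37.5%.

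A reader might also infer that the plan mixes a 120-minute average for new subjects with a 90-minute average for old ones. The documents do not say so. The 10 to 120 minute definition stands under the primary endpoint, and the only window attached to the group comparison is Ave90Clr, which matches the earlier data and can be computed from the planned scans. What remains is an ambiguity, because the list of secondary endpoints names no window.

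The 22 v 22 description in section 3.1 could be read as a concurrent-only analysis. It is not presented as a check, and section 3.3 says the 12 will be included.

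Finally, the proposed check is weak (steps 4 and 5). That stands, and it governs how the results should be read, but an imprecise unpooled estimate is still more informative than none.

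**Conclusion.** The point holds as a gap in the Stage 1 analysis that should be closed. Just over a third of any between-study shift (37.5%, or 35% with 34 controls) would enter the vaper versus non-vaper difference without adjustment, and no planned analysis would show how far the result depends on the earlier subjects. For assumed drifts of 2 to 4 points the bias is 0.75 to 1.5 points and type I error about 7% to 12%. These figures rest on SD 6, a two-sided test, 20 v 32 subjects and drift values that are assumptions, not findings.

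Two stronger conclusions are not supported: that the earlier controls are known to differ, or that pooling is invalid. The within-vaper comparison that forms the primary endpoint does not use these controls and is unaffected.

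**What to change.** Keep the pooled analysis, and before unblinding add to section 5.3:

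1. The Stage 1 difference using concurrent controls only, with its confidence interval, reported beside the pooled estimate. State its power: about 0.64 at 20 v 20 and 0.68 at 22 v 22.
2. The old-minus-new control difference with its confidence interval, labelled descriptive. State that a non-significant difference will not be taken as evidence that the two sets are exchangeable, and that it will not decide whether to pool.
3. One clearance window for every Stage 1 subject. Ave90Clr is available for current subjects from the scans already planned and is the metric in the power statement.
4. One control count, used consistently in the synopsis and sections 3.1, 3.3 and 5.4, with a sentence on whether the 12 earlier subjects met the present entry criteria.

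The cost is one extra model run and a few sentences of text. The downside is precision: the standard error rises from 1.71 to 1.90 at 20 v 20, and the check would often miss small drifts, so it supports the pooled result and does not replace it.
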